#### 10.3.3 Analysis of the Secondary Endpoint(s)

Secondary endpoint (1) will be a descriptive analysis of Sensitivity, Specificity, Positive Predictive Value, and Negative Predictive Value, using the histopathology results as the gold standard. We will assess potential difference or advantages in terms of: a) enhanced telemedicine diagnostic system; b) telemedicine Nevisense alone; c) telemedicine clinical + dermoscopy alone; and d) in-person dermatologist diagnosis. Sensitivity, Specificity, Positive Predictive Value, and Negative Predictive Value will be reported with an upper and lower confidence interval. Lesions with missing data will not be included in the relevant analyses (see Study Design schematic footnote 3). Participants lost to follow-up for reporting his/her biopsy results will be included in the analysis as the data required for analysis has been collected.

As another secondary endpoint, we will be evaluating the enhanced telemedicine service's impact on patient centered outcomes. Descriptive statistics for this secondary endpoint (2) (patient questionnaires, Supplement L will be presented as percentages. Study completion questionnaires may be qualitatively analyzed for themes and quantified by thematic representation across participants. Participant agreement of thematic categories will be calculated as percentages as a summary measure. Factors for stratification may include participants with a biopsy procedure and those without biopsy procedure as well as diagnosis of malignancy or benign lesion within those with biopsy. Participants with missing study completion questionnaire results due to inadequate duration of phone call will not be included.

As a final secondary endpoint (3), we will estimate the number of lesions that may benefit from the additional information of the Nevisense score to the clinical and dermoscopic exam. This estimation will be provided by the in-person dermatologist, and separately by each of the three teledermatologists (Supplement T & U). The estimates will be expressed as percentages. Any lesion with missing data in the in-person dermatologist and teledermatologist plan will not be included in analysis. Participants lost to follow-up will still be included in analysis of this endpoint as required data for this endpoint determination has been captured in the first visit.

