### **2.3 Rationale**

Detection of melanoma at its earliest stages is associated with high surgical cure rates, without the need for additional, potentially toxic and expensive systemic therapies. Rural and other medically underserved communities have higher rates of melanoma mortality that is associated with reduced access to dermatologic diagnostic services. We aim to study the effectiveness of an augmented telemedicine diagnostic platform for melanoma and other skin cancers that can potentially be deployed in pharmacies and urgent care centers that would be more available in rural communities than dermatologist offices.

The study will evaluate participant-selected lesions of adults in the New York City metropolitan area to simulate the walk-in clinic or pharmacy community setting. The control is an in-person evaluation by a community dermatologist, the current gold

standard. We aim to assess the sensitivity and specificity of the platform compared to the in-person dermatological examination in the diagnosis of melanoma and other skin cancers. Since the Nevisense evaluation is one component of the platform, and the current FDA approval is for it to be used in dermatologist offices to aid in biopsy decisions, we will also examine the degree to which teledermatologists can use the clinical and dermoscopy images to evaluate whether each study lesion would have been appropriate for the Nevisense evaluation had they seen the patient in-person. Finally, we will examine whether the combined teledermoscopy/clinical images plus Nevisense will have greater sensitivity and specificity to diagnose melanoma and other skin cancers than either approach alone.

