## 4 Study Design and Endpoints

### 4.1 Description of Study Design

**4.2 This is a prospective pilot study of a store-and-forward telemedicine diagnostic assessment of participant-selected skin lesions concerning for skin cancer, controlled against an in-person dermatologist assessment (gold standard evaluation). The study will be a single arm design with each participant undergoing telemedicine data acquisition (i.e. clinical and dermoscopic imaging and Nevisense measurement), immediately followed by the in-person dermatologist assessment. The in-person dermatologist will be blinded to the Nevisense score at the time of the visit. Using the telemedicine data, the teledermatology team will render a biopsy/no-biopsy recommendation within 3 business days of the participant evaluation. They will be blinded to the results of the in-person dermatologist's diagnostic evaluation. Study Endpoints**

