## 10 Statistical Considerations

### 10.1 Statistical Hypotheses

Primary endpoint:

We will not perform hypothesis testing in this pilot study; we will use descriptive statistics and summarize preliminary evidence from this pilot study.

Secondary endpoints

We will not perform hypothesis testing in this pilot study.

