### 10.2 Analysis Datasets

All eligible lesions evaluated by both the teledermatologists and the in-person dermatologist.

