#### 10.3.2 Analysis of the Primary Efficacy Endpoint(s)

To determine the agreement between in-person recommendation and the telemedicine (tele) recommendation we can calculate the number of discordant benign vs. malignant diagnoses; specifically, the number of subjects that were recommended a biopsy from the in-person dermatologist but were recommended no biopsy from the teledermatology team, and the number of subjects that were recommended no biopsy from the in-person dermatologist but biopsy by the teledermatologist team. We can calculate the Kappa coefficient as a measure of the degree of concordance or agreement with confidence intervals. We can also calculate "sensitivity" and "specificity" of the tele method assuming in-person diagnosis as the gold standard. Similarly, we can separately evaluate the agreement between in-person and: 1) dermoscopy alone; and 2) Nevisense (EIS score  $\geq 4$ ) without dermoscopy. We will also estimate the improvement (if any) of using both methods compared to one method. We expect the Kappa coefficient to be close to one, and high "sensitivity" and "specificity" (close to 1) for the SpotCheck method assuming in-person diagnosis as the gold standard.

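### Sections 10.3.2 and 10.3.3 set out to compare methods, but no difference between methods is given an interval and the estimates being compared may rest on different lesions

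*Combined protocol and SAP*

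**What the plan says.** Comparison between methods is a stated question. Section 2.3 says "we will examine whether the combined teledermoscopy/clinical images plus Nevisense will have greater sensitivity and specificity" than either component alone, and Section 3.2, item 1, sets the telemedicine method and its components against the in-person dermatologist. In the analysis sections:

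- Section 10.3.3, with histopathology as reference: "We will assess potential difference or advantages in terms of: a) enhanced telemedicine diagnostic system", followed by Nevisense alone, clinical plus dermoscopic imaging alone, and the in-person diagnosis. The uncertainty planned is: "Sensitivity, Specificity, Positive Predictive Value, and Negative Predictive Value will be reported with an upper and lower confidence interval".
- Section 10.3.2, with the in-person decision as reference: counts of telemedicine versus in-person discordance in each direction, and kappa with confidence intervals. It adds: "We will also estimate the improvement (if any) of using both methods compared to one method". No estimator or interval is named for that improvement.
- Section 4.1: "The study will be a single arm design with each participant undergoing telemedicine data acquisition", followed at once by the in-person assessment. The calls are therefore made within the same lesions.
- Section 10.2 defines the analysis set as: "All eligible lesions evaluated by both the teledermatologists and the in-person dermatologist". A Nevisense score is not required.
- Footnote 3 of the design schematic and Sections 5.2 and 6.1.4 withhold Nevisense from several lesion types. Bleeding or ulcerated lesions also get no dermoscopic image. Section 10.3.3 drops a lesion with missing data only from the analyses it affects.
- Section 10.1: "We will not perform hypothesis testing in this pilot study; we will use descriptive statistics and summarize preliminary evidence from this pilot study".

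**The concern.** The questions asked are about differences: what Nevisense adds to imaging, and how telemedicine compares with the in-person dermatologist. Under the plan as written, a reader would have one estimate and interval per method and would have to compare them by eye. That is unsatisfactory in two ways.

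First, the estimates may describe different lesions. Nevisense alone can be evaluated only where a score was taken, while imaging alone can also be evaluated on acral, crusted or scarred lesions. Part of any apparent difference may then be case mix.

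Second, two calls on the same lesion are correlated. For sensitivity, specificity and agreement, the precision of a difference on common lesions depends on how many lesions the two methods classify differently, which separate intervals do not show. Combined telemedicine and imaging alone share most calls, so a real gain or loss from adding Nevisense could pass unnoticed. This matters for a pilot meant to inform larger studies, since discordant-pair counts are what a paired follow-up study would be sized on.

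**Working it through.** **The plan's own figures (Section 10.4).** 500 participants x 2 lesions = 1000 lesions. 10% of 500 to 1000 = 50 to 100 biopsies; 90% = 450 to 900 lesions not biopsied. All reproduce. Section 2.4.2 expects malignancy in about 2% of subjects: 0.02 x 500 = 10. Applying 2% to lesions instead, which is an assumption, gives 0.02 x 1000 = 20. Benign biopsied lesions are then roughly 50 - 10 = 40 to 100 - 20 = 80.

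**Formulas.** For two calls on the same n lesions, let b and c be the lesions positive by the first or the second method only.

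- Unpaired SE = sqrt(p1(1-p1)/n + p2(1-p2)/n)
- Paired SE = sqrt((b+c)/n - ((b-c)/n)^2) / sqrt(n)

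Separate intervals are exact binomial. Intervals for differences are Newcombe score intervals, except in the agreement example, where they are estimate +/- 1.96 SE. The documents give no cell counts, so every 2x2 split below is assumed, and none allows for several lesions per participant.

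**Specificity, combined versus imaging alone, 80 benign lesions.** Assume 64 called positive by combined and 56 by imaging, with b = 8 and c = 0. The nesting follows the footnote to the telemedicine decision algorithm, under which a lesion concerning on imaging is always recommended for biopsy. The false-positive fractions are 80% and 70%, so specificity is 20% and 30%.

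- Separate 95% intervals for the false-positive fraction: 69.6 to 88.1% and 58.7 to 79.7%, which overlap.
- Unpaired SE = sqrt(0.8 x 0.2/80 + 0.7 x 0.3/80) = 0.068; interval for the 10-point difference -3.4 to 23.0 points.
- Paired SE = sqrt(8/80 - 0.1^2)/sqrt(80) = 0.034; interval 2.9 to 17.4 points. The SE ratio is 2.03.
- If not nested (b = 12, c = 4): paired SE 0.049, ratio 1.40, interval 0.1 to 19.9 points.
- With 40 benign lesions (b = 4, c = 0): SE 0.096 unpaired against 0.047 paired; intervals -9.0 to 28.1 and -0.7 to 21.2 points.

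**Sensitivity, combined versus imaging alone.**

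| Cancers | Detected | b, c | Unpaired interval (points) | Paired interval (points) |
|---|---|---|---|---|
| 20 | 19 v 16 | 3, 0 | -7.1 to 37.0 | -5.3 to 36.3 |
| 10 | 9 v 8 | 1, 0 | -23.6 to 42.1 | -20.2 to 40.0 |

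Pairing barely alters either interval.

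**Telemedicine versus in-person sensitivity.** Assume 20 cancers: 14 called by both, b = 4, c = 2. Paired SE = sqrt(6/20 - 0.1^2)/sqrt(20) = 0.120; unpaired sqrt(0.9 x 0.1/20 + 0.8 x 0.2/20) = 0.112. Here separate intervals are slightly too narrow. This direction is to be expected: Section 7.1.1 provides biopsy when either side recommends it, so lesions called by neither have no histology.

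**Agreement with the in-person decision.** Assume all 1000 lesions have both calls, with combined agreeing in 95.0%, imaging in 94.0%, b = 14 and c = 4. Paired SE = sqrt(18/1000 - 0.01^2)/sqrt(1000) = 0.0042, against 0.0102 unpaired. The +1.0 point difference has interval +0.2 to +1.8 paired and -1.0 to +3.0 unpaired. This is an upper-end illustration, because not all lesions will have a Nevisense score.

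**PPV and NPV.** Joining the 80-benign and 20-cancer examples, PPV is 19/(19+64) = 19/83 for combined and 16/(16+56) = 16/72 for imaging. The denominators differ by method, so concordant lesions matter too and paired-proportion formulas do not apply.

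**The case against.** The strongest reply is that this is a descriptive pilot. The plan tests nothing, promises to estimate the improvement, and nowhere says how a difference is to be judged. All of that stands. A reader might infer that the methods will be compared by whether their intervals overlap, or by an independent-samples formula; the documents do not say so. Nor is a per-method interval wrong for that method's own accuracy, leaving aside clustering of lesions within participants.

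A reader might also infer that the design is fully paired, with all four methods reading every lesion. It is not: Nevisense, and for some lesions dermoscopy, is withheld. That makes a common lesion set more necessary.

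Pairing is not wholly neglected either. For telemedicine versus in-person, Section 10.3.2 already counts discordance in both directions, although in subjects, and gives kappa. What is missing for that contrast is an interval for the difference. For combined versus imaging or Nevisense alone there is neither a discordance count nor an interval.

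Finally, it would be too strong to say that the comparative objective cannot be answered. Point differences remain available, and for the main contrast the error is usually conservative. For sensitivity, the few cancers limit precision far more than the analysis does. None of this supplies an interval for any difference, and the absence of testing does not remove the need for one.

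**Conclusion.** The plan asks about differences between methods, gives none of them an interval, and allows the compared estimates to rest on different lesion sets. The case for correction is strongest for specificity and agreement in the combined versus imaging contrast. On assumed counts with 80 benign biopsied lesions, the unpaired SE of a specificity difference is about 1.4 to 2.0 times the paired one, enough to hide a 10-point difference. For sensitivity, with about 10 to 20 cancers, little is gained.

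These sizes rest on assumed 2x2 splits, on reading the decision algorithm (whose figure is not shown) as nested, and on treating lesions as independent. The omission itself rests on the text of Sections 10.3.2 and 10.3.3 and on none of those assumptions.

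**What to change.** In Sections 10.3.2 and 10.3.3, name three contrasts: combined versus imaging alone, combined versus Nevisense alone, and telemedicine versus in-person. For each:

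1. Restrict to lesions with both calls, and state how many lesions that leaves out and why.
2. Show the paired 2x2 table of calls by lesion, split by histology where available.
3. Report the paired difference in agreement, sensitivity and specificity with a 95% confidence interval from a bootstrap that resamples participants, so that one to three lesions per person are kept together.
4. Use the same participant bootstrap for differences in PPV and NPV; a paired score interval does not apply to them.

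With few cancers the bootstrap interval for sensitivity will be rough, and it collapses to zero width if no cancer is discordant. The counts should therefore always be shown beside it.

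The cost is SAP wording, some extra analysis and a smaller common lesion set. It is estimation and consistent with Section 10.1. It assumes that the imaging-only call is recorded separately from the combined call. That depends on the teledermatologist data collection form (Supplement U), which is not among the documents and should be checked.

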conduct the study completion questionnaire. In the event of three failed attempts to reach the participant regarding biopsy results, the participant will be sent a certified letter communicating the biopsy results and need for follow-up medical care (if needed) (Supplement F). In the event that we are unable to make contact with the subject to communicate the teledermatology recommendation, we will send a certified letter with the recommendation printed (Supplement G). ). In the event that the teledermatology team recommends a biopsy and a participant cannot be contacted to schedule the biopsy or does not show up for a scheduled biopsy appointment, we will send a certified letter instructing them to contact us (Supplement H). At any point during the participant's involvement in the study, they can reach the DCSU by telephone to contact study personnel with concerns regarding wound healing, results interpretation, etc. Medical issues will be referred to one of the physician site investigators (e.g. dermatology resident or attending medical monitor). For emergencies, participants may contact [name] with information provided in the emergency card. (Supplement H)

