### **7.3 Study Schedule**

As described below, the study schedule includes a variable number of visits that depend upon the outcome of the initial evaluation. Briefly, 3 outcomes are possible:

- 1) The lesion(s) is diagnosed as not suspicious for skin cancer by both the in-person dermatologist and telemedicine team, and no biopsy is recommended
- 2) The lesion(s) is diagnosed as not suspicious for skin cancer by the in-person dermatologist, but suspicious for skin cancer by the telemedicine team, and a biopsy is recommended when the telemedicine team results are communicated to the participant
- 3) The lesion(s) is diagnosed suspicious for skin cancer by the in-person dermatologist, and a biopsy is performed at the initial visit, or scheduled to be performed at a follow up visit. In this scenario, the recommendation of the telemedicine team will not be communicated to the participant since we do not yet know if a 'no biopsy' recommendation by the telemedicine team is a safe alternative to a 'biopsy' recommendation by the in-person dermatologist.

Based on the outcomes described above, the participant will have either 1 visit and 1 phone call (initial evaluation and follow-up phone call), or an additional visit for telemedicine recommended biopsy and an additional phone call with biopsy results.

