### 7.3.2 Enrollment/Baseline

#### Enrollment/Initial Visit (Visit 1, Day 1)

- Participant and lesion eligibility confirmed by study personnel
  - This is the formal study screening prior to official enrollment (i.e. signing informed consent)
- Participant given Key Information Sheet with an overview of the study (Supplement Q)
- Conduct informed consent procedure and obtain signed ICF, if not conducted electronically prior to visit
- Assign subject ID for participant
- Obtain demographic information, medical history, medication history as part of enrollment questionnaire (Supplement K). If not conducted electronically prior to visit
- Acquire clinical images, dermoscopic image, and Nevisense data for each lesion
  - Nevisense procedure: the lesion is cleansed with an alcohol wipe and the electrical impedance measurement is conducted using a spring-loaded probe and disposable electrode measuring 5mm x 5mm. The measurement takes <1 minute and the electrical impedance score (EIS) will be recorded. Larger lesions may require a second measurement at another location within the lesion.
  - Record any adverse events from the procedure
  - Neither participants nor the in-person dermatologist will be aware of the score.
- Study team will number the skin lesions using Devon Skin Marker to verify same lesion evaluated across all assessments including the in person dermatologist
- Fill out questionnaire assessing telemedicine evaluation experience so far (Supplement L)
- In-person dermatologist examination of lesion(s) using naked eye and dermoscopy
- If a biopsy is recommended by the in-person dermatologist, participant will be offered a skin biopsy procedure or offered a second appointment within 1-2 weeks for the biopsy procedure
  - If a biopsy is performed, the participant is given at-home instructions for wound care (Supplement R) and the expected wait time for the biopsy results
  - Alternatively, the participant can choose to have the procedure done at another facility. The signed ICF includes permission for the study team to obtain those medical records
  - Follow-up care to the skin biopsy will proceed per standard clinical practice and includes result communication, wound care monitoring, suture removal if applicable and recommendations for follow-up care.
- If a biopsy is not recommended by the in-person dermatologist, the participant is given the expected wait time for telemedicine recommendation phone call.

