### 7.3.3 Intermediate Visits

#### Phone Call: For Participants without a Skin Biopsy recommendation by the in-person dermatologist for at least 1 lesion (Day 4+/-2)

- Communicate telemedicine recommendation (Supplement M & N)
  - If a skin biopsy is recommended, schedule participant for another in-person visit at the DCSU for skin biopsy procedure.
  - Alternatively, the participant can choose to have the procedure done at another facility. The signed ICF includes permission for the study team to obtain those medical records
  - If a skin biopsy is not recommended, thank the subject for their participation
- Administer the study completion questionnaire (Supplement L)

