**10.3.5 Adherence and Retention Analyses**

Adherence is not applicable. Participation is defined as all subjects that enroll into the study. Study retention is defined as participants that complete all visits through the last visit (study completion questionnaire) out of the number of subjects enrolled. Participants lost to follow up include all those that were unable to be contacted for biopsy scheduling, wound check, or study completion questionnaire administration.

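### Secondary endpoint 1 compares telemedicine and in-person accuracy on biopsied lesions only, but lesions flagged only by telemedicine always need a later visit, and no analysis shows or bounds the effect of biopsies not done

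*Combined protocol and SAP*

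**What the plan says.** **Population and reference standard.** The Protocol Summary computes accuracy for skin cancer on biopsied lesions. Section 10.3.3 uses histopathology as the reference.

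**In-person route.** Under 7.3.2 the "participant will be offered a skin biopsy procedure or offered a second appointment within 1-2 weeks for the biopsy procedure". Section 7.3 likewise says "a biopsy is performed at the initial visit, or scheduled to be performed at a follow up visit".

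**Telemedicine-only route.** The recommendation is given by phone on Day 4±2. Section 7.3.3 then instructs: "If a skin biopsy is recommended, schedule participant for another in-person visit at the DCSU for skin biopsy procedure". That visit is on Day 7±2, or the participant may use an outside facility. Section 5.4 provides a certified letter for the case where "a participant cannot be contacted to schedule the biopsy or does not show up for a scheduled biopsy appointment".

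**Missing data.** Section 10.3.3 says "Lesions with missing data will not be included in the relevant analyses", with a pointer to note 3 of the study schematic. That note lists lesions that get no Nevisense score or no dermoscopic image. The same paragraph says "Participants lost to follow-up for reporting his/her biopsy results will be included in the analysis as the data required for analysis has been collected". Section 10.3.5 defines loss for retention purposes: "Participants lost to follow up include all those that were unable to be contacted for biopsy scheduling". Section 10.4 anticipates 2% lost and 4% missing overall, not split by who recommended the biopsy.

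No section reports biopsy completion by recommendation source, or adjusts or bounds the accuracy estimates for it.

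**The concern.** The issue is confined to lesions that were recommended for biopsy but have no histology. Lesions that neither method flagged are a separate and larger gap.

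Telemedicine can gain sensitivity over the in-person examination only through cancers that it alone flags, and its extra benign biopsies lie in the same cell. That cell is also the only one where biopsy at Visit 1 is impossible. It should not be empty, because under 6.1.4 one concerned teledermatologist out of three is enough for a recommendation.

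Each telemedicine-only cancer without histology removes a telemedicine true positive and an in-person false negative. Each telemedicine-only benign lesion without histology removes a telemedicine false positive and an in-person true negative. The distortion runs against telemedicine on sensitivity and in its favour on specificity. Section 10.3.1 gives the possibility that telemedicine is better on both as the reason for doing the pathology analysis.

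**Working it through.** **Plan figures (10.4, 2.4.2).** 500 × 10% = 50 and 1000 × 10% = 100 biopsies recommended, leaving 450 and 900 lesions; this matches 10.4. About 2% of 500 subjects with a malignancy gives about 10.

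**Assumed illustration.** Take 100 flagged lesions with 10 cancers and equal true accuracy. The split by cell is my assumption:

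| Cell | Lesions | Cancers | Benign |
|---|---|---|---|
| Both | 40 | 6 | 34 |
| Telemedicine only | 30 | 2 | 28 |
| In-person only | 30 | 2 | 28 |

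With full histology, sensitivity is 8/10 = 80% for each method, and specificity among flagged lesions is 28/90 = 31.1% for each.

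**Formulas.** Let c_t be histology completion in the telemedicine-only cell and c_i completion in the other two cells.

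- Sensitivity difference (tele − in-person) = (2c_t − 2c_i) / (8c_i + 2c_t)
- Specificity difference = (28c_i − 28c_t) / (62c_i + 28c_t)

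With c_i = 98%:

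| c_t | Sensitivity, tele v in-person | Difference | Specificity difference |
|---|---|---|---|
| 98% | 80.0% v 80.0% | 0 | 0 |
| 96% | 7.80/9.76 = 79.9% v 7.84/9.76 = 80.3% | −0.4 | +0.6 |
| 90% | 7.68/9.64 = 79.7% v 7.84/9.64 = 81.3% | −1.7 | +2.6 |
| 80% | 7.48/9.44 = 79.2% v 7.84/9.44 = 83.1% | −3.8 | +6.1 |
| 60% | 7.08/9.04 = 78.3% v 7.84/9.04 = 86.7% | −8.4 | +13.7 |

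Only the 96% row is close to the losses the protocol anticipates. With c_i at 100% it becomes −0.08/9.92 = −0.8 and +1.12/88.88 = +1.3. The 90%, 80% and 60% rows are assumptions.

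Telemedicine PPV at c_t = 60% is 7.08/57.2 = 12.4%, against a true 8/70 = 11.4%. In-person PPV is unaffected.

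**If telemedicine is truly better.** Assume 50 telemedicine-only, 10 in-person-only and 40 both, with cancers 3, 1 and 6 (90% v 70%). With c_i = 98%, the true 20-point advantage appears as 19.5, 18.0, 15.3 and 9.5 points at c_t = 96%, 90%, 80% and 60%.

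**One lost cancer.** In the first illustration, 8/10 v 8/10 becomes 7/9 = 77.8% v 8/9 = 88.9%, a difference of −1/9, or 11 points. If the two telemedicine-only cancers are lost independently, the chance of losing at least one is 1 − 0.96² = 8% at c_t = 96% and 1 − 0.80² = 36% at 80%.

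**Weighting check.** At c_t = 80% the cell has 1.6 verified cancers in expectation, and 1.6/0.80 = 2 restores the true count. This holds only if verification is random within the cell.

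**The case against.** - **Differential loss is inferred.** A reader might infer that missing histology is concentrated in the telemedicine-only cell. The documents do not show this. In-person biopsies can also be deferred or done elsewhere. Participants with no in-person recommendation are told to expect the telemedicine call (7.3.2). The protocol provides three calls, certified letters, access to outside records, and forfeited payment for not following through (5.4, 7.3.3, 15.3). This stands: the route is structurally harder, but completion is unknown.
- **The quoted sentence.** A reader might infer that 10.3.3 itself prescribes deletion for missing histology. Its pointer to schematic note 3 concerns missing test inputs. The restriction comes from analysing biopsied lesions against histology, and 10.3.3 has no explicit rule for recommended but unbiopsied lesions.
- **10.3.3 against 10.3.5.** A reader might see a contradiction, because 10.3.5 counts as lost people never reached to schedule a biopsy. The 10.3.3 sentence concerns people lost for reporting of biopsy results, who have already been biopsied and whose histology exists. The two sections are compatible.
- **The illustration may have too much discordance.** With 900 lesions flagged by neither, observed agreement is 0.94, chance agreement is 0.07² + 0.93² = 0.8698, and kappa is 0.0702/0.1302 = 0.54. Section 10.3.2 expects kappa close to one. Smaller discordant cells would make a loss less likely. The one-cancer artefact remains: with one cancer in each discordant cell, 9/10 v 9/10 becomes 8/9 v 9/9, again 11 points.
- **Over-biopsy is visible elsewhere.** The primary endpoint counts telemedicine-yes/in-person-no recommendations without histology, and 14.3 tracks the team's benign-to-malignant ratio. So over-biopsy would not be hidden; what is distorted is its measurement against pathology.
- **It is a descriptive pilot (10.1).** No error rate is at stake, but biased estimates could still mislead the larger studies this one is meant to inform.

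**Conclusion.** The point holds as a conditional bias that the plan neither measures nor bounds. If histology completion is lower for telemedicine-only lesions, restricting to biopsied lesions understates telemedicine sensitivity, overstates in-person sensitivity and removes telemedicine false positives. With equal completion across cells the comparison among flagged lesions is undistorted.

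At the anticipated 2-4% loss the expected shift is about 1 point, small beside the sampling error of about 10 cancers. The practical exposure is a single lost telemedicine-only cancer, worth about 11 points. These sizes rest on assumed cell splits and on about 10 cancers, taken from the 2% of subjects in 2.4.2. Larger shifts at 60-80% completion should not be read as predictions, since nothing in the documents supports those rates.

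**What to change.** In 10.3.3:

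1. Tabulate lesions recommended, biopsied and with histology, separately for both, telemedicine-only and in-person-only.
2. Beside the complete-case estimates, give sensitivity and PPV for both methods with every recommended but unverified lesion counted as benign, then as malignant. In the one-lost-cancer example this shows 7/9 v 8/9 and 8/10 v 8/10. If lesions are unverified in both discordant cells, these scenarios do not bound the sensitivity difference. Its extremes come from counting one discordant cell's unverified lesions as malignant and the other's as benign.
3. As a sensitivity analysis where cell counts allow, weight each verified lesion by the inverse of its cell's verification fraction, with participant-level bootstrap intervals. State the assumption of random verification within cells; with one to three cancers in a cell the result will be unstable.
4. State a rule for recommended but unbiopsied lesions, and say that all these estimates apply to flagged lesions only.

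The cost is SAP wording, minor programming and wider intervals. The inputs are the recommendations and pathology results already collected, and no study procedure changes.
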